### 4 Trial design

#### 4.1 Overall design

[figure not shown]
This non-commercial parallel group, placebo-controlled double blind design aims to make a preliminary assessment of the effectiveness of ketamine in promoting and prolonging abstinence in alcohol dependent patients (Fig. 1). *Why this design was chosen:* A parallel group design is chosen as a crossover would not be feasible with the long time-scales of the study, and given marked carry-over effects that occur in substance-use reduction studies. Three weekly doses of ketamine were chosen as this protocol showed effectiveness in the preliminary studies [33]. This approach has been chosen, rather than a full-scale trial as it is important to confirm the preliminary findings in alcohol dependence. We have chosen to assess outcomes at 3 months and 6 months as from examining other pharmacological and non-pharmacological trials, the largest change in drinking behaviour occurs in the first 3 months and then tails off [40]. However we will follow up again at 6 months to index maintenance of the treatment effect (balancing against the issues of retention of patients in the trial).

For the purpose of this study, Relapse: 5 drinks (drink=13g) in men (8.1units) and 4 drinks (6.5 units) in women on any single occasion and Lapse is defined as 'any other episode of alcohol consumption'.

*Blinding to the IMP:* The trial design will be double blinded. This has been chosen so as to reduce any bias from the power of suggestion of which treatment the patient is received by both the researchers and the patient. The pharmacy or delegated unblinded personnel at both sites will prepare

the syringe for infusion in a blinded fashion so that the administering anaesthetist, psychological researcher and patient are all blind to treatment allocation.

Figure 1: Schematic of overall trial design from recruitment to end of follow up

## **5 Selection of Subjects**

### **5.1 Inclusion criteria**

1. 18 – 65 years old
2. Meet either a) DSM-5 criteria for moderate/severe alcohol use disorder or b) DSM-IV criteria for alcohol abuse/dependence (see Appendix A) within the last 12 months
3. Currently abstinent from alcohol (breathlyser BAC level 0.00) and negative urine drug screen (participants testing positive for THC who do not have a history or current cannabis dependency may be included; participants testing positive for benzodiazepines who do not have a previous or current diagnosis of benzodiazepine dependence/severe use disorder may be included)
4. Capacity to give informed consent as defined by GCP guidelines
5. Willing to wear SCRAM-X bracelet for active treatment
6. Females of childbearing potential and males must be willing to use an effective method of contraception (hormonal or barrier method of birth control; True abstinence) from the time consent is signed until 6 weeks after treatment discontinuation and inform the trial if pregnancy occurs. For the purpose of clarity, True abstinence is when this is in line with the preferred and usual lifestyle of the subject. Periodic abstinence (e.g., calendar, ovulation, symptothermal, post-ovulation methods), declaration of abstinence, withdrawal, spermicides only or lactational amenorrhoea method for the duration of a trial, are not acceptable methods of contraception.
7. Females of childbearing potential must have a negative pregnancy test within 7 days prior to being registered for trial treatment and on day of first treatment.

### **5.2 Exclusion criteria**

1. Currently taking any other relapse prevention medication or anti-depressants
2. Current uncontrolled hypertension, systolic 140mm Hg or greater and diastolic 90mm Hg or greater
3. Currently has BMI outside normal limits <16 or > 35
4. Any relevant mental or physical health issues as determined by medically qualified personnel, which may include:
  - a. Current or history of psychosis as identified by DSM-5 or DSM-IV SCID
  - b. Current or historical diagnosis of schizophrenia in a first degree relative

- c. Co-morbid current psychiatric diagnosis excluding depression and anxiety.
  - d. Previous or current diagnosis of a substance dependence / severe substance misuse disorder as confirmed by the participant's GP or if the participant has sought professional help for their dependence
  - e. Clinically relevant history of neuropsychological difficulties
  - f. One or more previous medically confirmed seizures including seizures witnessed by an appropriate clinician, documented evidence from an EEG or a history consistent with a diagnosis of an epileptiform illness
  - g. Current suicidal ideation, as judged clinically
5. Any medication deemed, by the trial medical professionals, to pose risk combined with ketamine which may include daily prescribed use of:
- a. Barbiturates and/or narcotics
  - b. Atracurium and tubocurarine
  - c. Central nervous system (CNS) depressants (e.g. phenothiazines, sedating H1 – blockers or skeletal muscle relaxants)
  - d. Thiopental
  - e. Thyroid hormones
  - f. Antihypertensive agents
  - g. Theophylline and methylxanthine
6. Liver function tests that assess chronic liver damage (namely bilirubin, ALT, AST) > 3 times normal levels
7. Where there are "Special warnings and precautions for use" according to the SPC and where risk vs benefit ratio is not in favour of giving ketamine, with assessment made by physical examination by medically qualified trial personnel, self-report or inspection of the medical notes. Current diagnosis of:
- a. Acute intermittent porphyria
  - b. Dehydration or hypovolemia
  - c. Hyperthyroidism
  - d. Pulmonary or upper respiratory tract infection
  - e. Severe Coronary artery disease, Cerebrovascular accident or cerebral trauma
  - f. Known glaucoma or globe injuries

- g. Cirrhosis
  - h. Epilepsy
  - i. Intracranial mass lesions, hydrocephalus, or presence of head injury (i.e. evidence of lasting impact of head injury that is affecting everyday functioning)
8. Not willing to use effective contraception or (females) take pregnancy test
  9. Allergic reaction to ketamine
  10. >10 previous inpatient detoxifications from alcohol
  11. Pregnant or Breastfeeding
  12. Allergies to excipients of IMP and placebo
  13. Use of another experimental investigational medicinal product that is likely to interfere with the study medication within 3 months of study enrolment.

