- Currently abstinent from alcohol (breathlyser BAC level 0.00) and negative urine drug screen (participants testing positive for THC who do not have a history or current cannabis dependency may be included; participants testing positive for benzodiazepines and who do not have a history or current dependency for benzodiazepines may be included);
- Capacity to give informed consent as defined by GCP guidelines;
- Willing to wear SCRAM-X bracelet for active treatment;
- Females of childbearing potential and males must be willing to use an effective method of contraception (hormonal or barrier method of birth control; True abstinence) from the time consent is signed until 6 weeks after treatment discontinuation and inform the trial if pregnancy occurs. For the purpose of clarity, True abstinence is when this is in line with the preferred and usual lifestyle of the subject. Periodic abstinence (e.g., calendar, ovulation, symptothermal, post-ovulation methods), declaration of abstinence, spermicides only, withdrawal or lactational amenorrhoea method for the duration of a trial, are not acceptable methods of contraception;
- Females of childbearing potential must have a negative pregnancy test within 7 days prior to being registered for trial treatment and on day of first treatment.

Main Exclusion Criteria:

- Currently taking any other relapse prevention medication or anti-depressants;
- Current uncontrolled hypertension (systolic 140mm Hg or greater and diastolic 90mm Hg or greater);
- Currently has BMI outside normal limits <16 or > 35
- Any relevant mental or physical health issues as determined by medically qualified personnel, which may include:

- Current or history of psychosis as identified by DSM-5 or DSM-IV SCID;
  - Current or historical diagnosis of schizophrenia in a first degree relative;
  - Current co-morbid psychiatric diagnosis excluding depression and anxiety;
  - Previous or current diagnosis of substance dependence / severe substance misuse disorder as confirmed by the participant's GP or if the participant has sought professional help for their dependence;
  - Clinically relevant history of neuropsychological difficulties. One or more previous medically confirmed seizures, including seizures witnessed by an appropriate clinician, documented evidence from an EEG or a history consistent with a diagnosis of an epileptiform illness;
  - Current suicidal ideation, as judged clinically.

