## 2.5 Assessment and management of risk

This trial is categorised as TYPE B suggesting that the risk is somewhat higher than the risk of standard medical care. The IMP is licenced in the EU but is being trialled in a new indication

The table below summarises the risks, frequencies and mitigations of the IMP:

Potential risk	Risk Frequency *	Risk Management
Elevation of blood pressure, respiratory and heart rate	Common	
IMP will be administered at site. Vital signs will be monitored throughout the infusion of ketamine. Patients will not leave the site until they are judged 'street ready' by an anaesthetist, all signs of acute intoxication are absent and they will be advised to be collected by a responsible adult or transportation will be arranged for them. At discharge patients will be given a 24 hour contact card for emergencies.
 
Patients with uncontrolled hypertension, eclampsia or pre-eclampsia, severe coronary or myocardial disease, cerebrovascular accident or cerebral trauma will be excluded from the study (see section 5.2).
 
Patients taking thyroid hormones have an increased risk of developing hypertension and tachycardia when given with ketamine and therefore we will exclude these patients (see section 5.2).

Bradycardia, Arrhythmia,	Uncommon	IMP will be administered at site. Vital signs (heart rate, blood pressure, pulse oximetry)

Hypotension		
will be monitored throughout the infusion of ketamine. Patients will not leave the site until they are judged 'street ready' by an anaesthetist, all signs of acute intoxication are absent and they will be advised to be collected by a responsible adult or transportation will be arranged for them. At discharge patients will be given a 24 hour contact card for emergencies.
 
Patients with uncontrolled hypertension, eclampsia or pre-eclampsia, severe coronary or myocardial disease, cerebrovascular accident or cerebral trauma will be excluded from the study (see section 5.2).
 
Concomitant use of antihypertensive agents increases risk of hypotension and therefore, patients on antihypertensive agents will be excluded from the study (see section 5.2).

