***Screening Visit (Visit 1 Day 28 to 1 days before visit 2 (baseline) visit):***

Formal screening will take place at this screening visit as set out in Appendix B and listed below. The methods of the assessments are explained in section 7.9. Consent will be taken from the patient prior to the assessments at this visit (see section 7.1).

Following screening and eligibility determination, those still meeting criteria for inclusion in the study can be fitted with the SCRAM-X bracelet anytime between the screening visit and visit 2. A date for visit 2 will be arranged, within 28 days of the screening date.

The visit schedule is set out below and as a chart in Appendix B:

- I. Trial Discussion
- II. Informed Consent
- III. Medical history
- IV. Physical Examination (repeat screens of height and weight may be conducted if initial results do not fall within boundaries described in 5.2 but patient meets other criteria for eligibility)
- V. SCID
- VI. Vital Signs (repeat screens of blood pressure may be conducted if initial results do not fall within boundaries described in 5.2 but patient meets other criteria for eligibility)
- VII. Bloods to assess eligibility (U&Es, LFTs, FBC; repeat screens may be conducted every 7days if initial results do not fall within boundaries described in 5.2 but patient meets other criteria for eligibility, see Appendix B and section 7.9.2 for details of the tests that will be used).
- VIII. Eligibility Determination
- IX. Urine Drug Screen (repeat screens may be conducted if initial results do not fall within boundaries described in 5.2 but patient meets other criteria for eligibility, see Appendix B and section 7.9.2 for details of the tests that will be used)
- X. Pregnancy test in WOCBP (urine test)
- XI. Breathalyser (repeat breathalyser screens may be conducted if initial result does not fall within boundaries described in 5.1 but patient wishes to continue with detoxification and return once they are abstinent)
- XII. Routine SCRAM-X fitting (unless study team deem this not possible)
- XIII. Concomitant medication review
- XIV. Alcohol and Drug Use History
- XV. BDI
- XVI. HAM-D
- XVII. Columbia Suicide Severity Rating Scale
- XVIII. Reasons for drinking questionnaire
- XIX. STAI
- XX. ACQ-NOW

- XXI. BPRS
- XXII. PSI
- XXIII. Alcohol Timeline Follow Back

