#### **7.5 Baseline assessments (Visit 2, 1 to 28 days after screening):**

The methods of the assessments are described in detail in section 7.9.

- I. Vital Signs (see Appendix B and section 7.9.2 for details of the tests that will be used). Vital signs will be continuously monitored throughout the infusion until the participant has recovered. This monitoring will be recorded on a standard observation chart, stored as source data. The eCRF will record 3 sets of readings, one prior to the infusion, another after the infusion terminates, and then finally after the participants recovery.
- II. Bloods, blood samples for BDNF and ketamine will be obtained pre-IMP/placebo administration and post IMP administration (see Appendix B and section 7.9.2 for details of the tests that will be used.)
- III. Full eligibility determination
- IV. Urine Drug Screen (see Appendix B and section 7.9.2 for details of the tests that will be used.)
- V. Pregnancy test in WOCBP (urine test)
- VI. Breathalyser
- VII. Randomisation
- VIII. IMP/placebo Administration (see section 7.6)
- IX. SCRAM-X checks (if already fitted) / alternative SCRAM-X fitting (where routine fitting at screening not completed)
- X. Relapse Prevention Based Cognitive Behavioural Therapy
- XI. Adverse Events Review

- XII. Concomitant medication review
- XIII. BDI
- XIV. HAM-D
- XV. POMS
- XVI. STAI
- XVII. ACQ-NOW
- XVIII. BPRS
- XIX. PSI
- XX. Alcohol Timeline Follow Back
- XXI. Fagerstrom Nicotine Dependence
- XXII. Craving VAS
- XXIII. SF-12
- XXIV. Prose Recall
- XXV. Delay Discounting (monetary choice questionnaire)
- XXVI. Stop Signal Reaction time
- XXVII. Working memory (digit span WAIS-IV)
- XXVIII. Adverse Effect VAS( e.g. nausea, intoxication, anxiety, memory : 20 mins before infusion and every 20 mins for next 2 hours)
- XXIX. Pattern Recognition Memory Test

**7.6 Treatment procedures (visits 2 (i.e. baseline; 1 to 28 days after screening), visit 4 (4 to 21 days after visit 2) and 6 (4 to 21 days after visit 4))**

IMP Dosing Patients will receive 3 x weekly infusions of ketamine (Ketalar®) (0.8mg/kg made up to 50ml with saline over 40 minutes) or 3 x weekly infusion of placebo (0.9% saline over 40 minutes). The drug/placebo will be prepared in a blinded fashion by pharmacy (who are unblinded) or delegated unblinded site staff on the ward at site and will be administered by the research anaesthetist at the Clinical Research Facility at sites who will remain blinded.

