Breathalyser tests will be used at each visit for the following reasons:

- Screening & re-screening – To assess eligibility
- Baseline visit (1st infusion) – To assess eligibility/ensure safety of IMP administration/ensure patient is able to complete cognitive tasks and questionnaires, as well as engage with therapy/education
- Visit 3, 5, 7 & 8 – To ensure patient is able to complete cognitive tasks and questionnaires, as well as engage with therapy/education
- Visit 4 & 6 (2nd & 3rd infusion) – To ensure safety of IMP administration/ensure patient is able to complete cognitive tasks and questionnaires, as well as engage with therapy/education
- Visit 9 & 10 - To ensure patient is able to complete cognitive tasks and questionnaires

Once randomised, if a patient attends for any visit and does not blow 0 on the breathalyser the visit will be terminated (either for the primary purpose of safety on infusion visits or of data integrity on non-infusion visits) and the patient invited to re-attend to complete the visit within the allocated visit window.

Concomitant Medication: All prescription medication, over-the-counter medication, vitamins, and/or herbal supplements will be recorded on case report forms (CRFs).

Vital Signs: Resting pulse, pulse oximetry and blood pressure (BP) measurements will be measured at each visit phase for safety monitoring. Vital signs will be continuously monitored throughout the infusion until the participant has recovered. This monitoring will be recorded on a standard

observation chart, stored as source data. The eCRF will record 3 sets of readings, one prior to the infusion, another after the infusion terminates, and then finally after the participants recovery.

Physical Examination: Height, weight and oral/tympanic temperature will be recorded.

At screening a physician will perform a physical examination of the cardiovascular, respiratory, GI and neurological system to a level of detail that would be expected for a patient due to receive anaesthesia.

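### The blood pressure exclusion joins its two limits with *and*, so it misses isolated systolic or diastolic elevation of any size

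*Protocol*

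**What the plan says.** Section 5.2, criterion 2, lists as an exclusion "Current uncontrolled hypertension, systolic 140mm Hg or greater and diastolic 90mm Hg or greater". The Summary's main exclusion criteria place the same limits in brackets after the same clinical term: "systolic 140mm Hg or greater and diastolic 90mm Hg or greater". Both places use *and*.

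Section 2.5 lists raised blood pressure as a common risk of ketamine. Part of its stated mitigation, with a cross-reference to Section 5.2, is: "Patients with uncontrolled hypertension, eclampsia or pre-eclampsia, severe coronary or myocardial disease, cerebrovascular accident or cerebral trauma will be excluded from the study".

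Section 7.4 (Screening Visit, vital signs) gives no limit of its own and refers back: "repeat screens of blood pressure may be conducted if initial results do not fall within boundaries described in 5.2".

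**The concern.** An exclusion for high blood pressure would normally apply when either component is too high. Joined by *and*, the limits exclude only patients in whom both are raised, so a large elevation in one component passes criterion 2 whenever the other sits just under its limit.

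What is at stake is patient safety. The numeric rule does not reach isolated systolic or isolated diastolic elevation, so for those patients exclusion depends on individual medical judgement with no stated value to judge against. The drug in question has a rise in blood pressure among its listed common effects (Section 2.5 and Appendix C). Raised readings are also foreseeable in this population: the retest list in Section 7.4 names recent alcohol withdrawal as a cause.

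**Working it through.** The plan reports no figure to reproduce here. The check is a truth table, followed by a search for any other blood pressure limit.

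**Inputs.** Systolic limit 140 mm Hg, diastolic limit 90 mm Hg, joined by *and* (Section 5.2, criterion 2; Summary). The example readings are illustrative and do not come from the documents.

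**Rules compared.**
- As written: exclude if SBP ≥ 140 *and* DBP ≥ 90.
- Alternative: exclude if SBP ≥ 140 *or* DBP ≥ 90.

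| Reading | SBP ≥ 140 | DBP ≥ 90 | As written (*and*) | With *or* |
|---|---|---|---|---|
| 140/90 | yes | yes | excluded | excluded |
| 190/88 | yes | no | not excluded | excluded |
| 138/115 | no | yes | not excluded | excluded |
| 139/89 | no | no | not excluded | not excluded |

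As written, 1 of the 4 readings is excluded; with *or*, 3 of the 4 are.

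**Size of the gap in the examples.**
- 190/88: 190 − 140 = 50 mm Hg above the systolic limit, and 90 − 88 = 2 mm Hg below the diastolic limit.
- 138/115: 115 − 90 = 25 mm Hg above the diastolic limit, and 140 − 138 = 2 mm Hg below the systolic limit.

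In each case 2 mm Hg below one limit cancels a large excess over the other. In general, the two rules differ exactly where one component is at or above its limit and the other is below. Criterion 2 as written puts no ceiling on the raised component in that region.

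**Is there another limit elsewhere?**
- Section 7.4, screening visit: points back to Section 5.2. Read literally, 190/88 lies within those boundaries, so it does not trigger the repeat reading either.
- Section 7.4, retest list: allows a retest for inflated blood pressure, with no number.
- Section 5.2, criterion 4: "Any relevant mental or physical health issues as determined by medically qualified personnel" may exclude, with no blood pressure value.
- Section 7.9.1: the screening examination is "to a level of detail that would be expected for a patient due to receive anaesthesia", with no blood pressure value.
- Sections 7.5 and 7.7: "Vital signs will be continuously monitored throughout the infusion until the participant has recovered" at baseline, and likewise at visits 4 and 6. A pre-infusion reading is recorded, but no value is set for withholding the infusion.
- Sections 7.11.1 and 9.11: no blood pressure limit for stopping treatment, and no dose modification permitted.

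Criterion 2 is therefore the protocol's only numeric blood pressure safeguard.

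**Exposure.** Allocation is 1:1:1:1 over four groups, two of which receive ketamine, so a patient entered this way has a 2/4 = 50% chance of ketamine, with up to three infusions.

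**The case against.** The strongest reply is that the operative term is uncontrolled hypertension and the numbers only gloss it. The Summary puts them in brackets, and Section 2.5 excludes the condition without requiring both components to be raised. A medically qualified screener could exclude 190/88 under the clinical term alone. The retest list in Section 7.4 also treats inflated blood pressure as an eligibility problem without asking for both components.

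There are further safeguards. Daily antihypertensive use may exclude under criterion 5(f), and Section 2.5 says such patients will be excluded. Criterion 7 weighs risk against benefit for the listed precautions, although hypertension is not among them. Vital signs and eligibility are checked again at visit 2. An anaesthetist gives the drug, and the investigator may stop treatment for any reason. The dose is 0.8 mg/kg over 40 minutes, below the anaesthetic range quoted in Section 2.4. Many clinicians would stop a patient at 190/88.

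That much stands: these checks make it less likely that such a patient is infused. They do not repair the criterion. None supplies a limit, monitoring during the infusion acts only after the drug has started, and a screener who excludes 190/88 must set aside the numbers that define the term. If the wording can reasonably be read either way, the two sites may apply it differently.

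Two other points are fair. The 1-of-4 and 3-of-4 counts depend on the readings chosen and say nothing about frequency. And *or* also excludes mild single-component readings such as 140/75 or 125/90, so it tightens entry for some patients. The retest provisions in Section 7.4 limit that loss for situational readings.

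**Conclusion.** The concern holds. As literally written, criterion 2 excludes 140/90 but not 190/88 or 138/115, and no other part of the protocol sets a blood pressure limit. The mitigation in Section 2.5 therefore rests on a criterion that does not reach isolated elevation of either component.

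The conclusion rests on the literal wording, which is the same in both places. It does not claim that any such patient was or would be enrolled. The number affected cannot be derived, because the documents give no blood pressure distribution. Clinical oversight partly offsets the gap, so this is a point that should be fixed rather than one that undermines the trial. It does not touch the statistical analysis.

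**What to change.** In Section 5.2, criterion 2, and in the Summary, replace *and* with *or*: exclude if systolic is 140 mm Hg or above **or** diastolic is 90 mm Hg or above. Keep the repeat-reading and retest provisions in Section 7.4. Section 2.5 then needs no change, because the criterion it cites delivers what it says.

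If the sponsor does not want to exclude mild single-component readings, the alternative is to keep the present rule and add an explicit higher ceiling for each component alone. The documents offer no figure for such a ceiling, so the sponsor would have to choose and justify one. Changing to *or* uses limits the protocol already contains and is simpler.

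The edit is one word in two places. It would bring some additional repeat readings or screen failures, in a number that cannot be derived from the documents. It would also need the amendment handling in Section 16: the sponsor classifies the change and, if it is substantial, ethics, regulatory and R&D approval must come before it is used.
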